## 6.6.4 Tumor Lysis Syndrome

Tumor lysis syndrome (TLS) has been associated with the treatment of CLL and other B-cell neoplasms, including venetoclax treatment which requires a dose escalation of the drug over 5 weeks to mitigate TLS risk. It is unknown whether combination RP-3500 and olaparib will induce TLS upon initiation of treatment. Therefore, TLS prophylaxis with a xanthine oxidase inhibitor will be administered at least 72 hours prior to C1D1 and during the first cycle of study therapy.

TLS blood chemistry monitoring are mandated at screening, C1D1, C1D2, C1D3, C1D8, C1D15, and C2D1. After which, TLS monitoring is at the discretion of the treating provider. If rasburicase is being considered for the treatment of hyperuricemia, it is recommended to check for red blood cell levels of glucose-6-phosphate dehydrogenase (G6PD) as rasburicase administration in G6PD-deficient patients may cause severe hemolysis.

Event	Hyperkalemia (including rapidly rising potassium)	
Potassium ≥ 0.5 mmol/L increase from prior value (and ≤ULN)	
 
Hold RP-3500 and olaparib. Recheck potassium, phosphorous, uric acid, calcium, and creatinine in 1 hour.
 
If additional ≥ 0.2 mmol/L increase in potassium, but still ≤ upper limit of normal (ULN), manage per potassium > ULN.
 
o If < 0.2 mmol/L increase in potassium and potassium ≤ ULN and no other evidence of tumor lysis, resume camonsertib (RP-3500) and olaparib per protocol
 
	
Potassium > ULN but < 6 mmol/L (6.0mEq/L) and asymptomatic (e.g. muscle cramps, weakness,	
 
Hold camonsertib (RP-3500) and olaparib until resolution to ≤ ULN.
 
Perform ECG; administer calcium gluconate 100-200 mg/kg IV slowly if there is evidence of life-threatening arrhythmias         
 
Administer Kayexalate/Resonium 60g if available
 
Administer furosemide 20mg
 
 
 
	

For blood chemistry changes or symptoms suggestive of TLS in cycle 1:

paresthesias, nausea, vomiting, and diarrhea)	
 
Recheck potassium, phosphorous, uric acid, calcium and creatinine in 1 hour after administration of calcium gluconate, keyexalate/resonium, furosemide and ECG. If potassium ≤ULN 1 hour later, repeat potassium, phosphorous, uric acid, calcium, and creatinine 1, 2, and 4 hours later, if no other evidence of tumor lysis.
 
	
Potassium ≥ 6 mmol/L (6.0mEq/L) and symptomatic (e.g. muscle cramps, weakness, paresthesias, nausea, vomiting, and diarrhea)	
 
Hold camonsertib (RP-3500) and olaparib until resolution to ≤ ULN.
 
Perform ECG; administer calcium gluconate 100-200 mg/kg IV slowly if there is evidence of life-threatening arrhythmias         
 
Administer Kayexalate/Resonium 60g if available
 
Administer furosemide 20mg IV
 
Administer insulin 0.1 U/kg IV + D52 2 mL/kg IV
 
Administer sodium bicarbonate 1 to 2 mEq/kg IV. Rasburicase should not also be used as this may exacerbate calcium phosphate precipitation.
 
Recheck potassium, phosphorous, uric acid, calcium and creatinine every hour.
 
 
 
	
Event	Hyperuricemia	
Uric acid ≥ 8.0 mg/dL (476 µmol/L)	
 
Hold camonsertib (RP-3500) and olaparib until resolution to < 8.0 mg/dL (476 µmol/L)
 
Give rasburicase (as per local guidelines). Sodium bicarbonate should not be used as this may exacerbate calcium phosphate precipitation.
 
Recheck potassium, phosphorous, uric acid, calcium, and creatinine in 1 hour after rasburicase administration.
 
	
Uric acid ≥ 10 mg/dL (595 µmol/L) OR Uric acid ≥ 8.0 mg/dL (476 µmol/L) with 25% increase and creatinine increase ≥ 0.3 mg/dL (≥ 0.027 mmol/L) from predose level.	
 
Hold camonsertib (RP-3500) and olaparib until resolution
 
Give rasburicase (as per local guidelines). Sodium bicarbonate should not be used as this may exacerbate calcium phosphate precipitation.
 
Recheck potassium, phosphorous, uric acid, calcium, and creatinine in 1 hour after rasburicase administration.
 
If uric acid < 8.0 mg/dL 1 hour later, repeat potassium, phosphorous, uric acid, calcium, and creatinine 2 and 4 hours later, if no other evidence of tumor lysis.
 
	
Event	Hypocalcemia	
Corrected calcium ≤ 7.0 mg/dL (1.75 mmol/L) OR Patient symptomatic (e.g., muscle cramps,	
 
Hold camonsertib (RP-3500) and olaparib until resolution of calcium to > 7.0 mg/dL (1.75 mmol/L) or resolution of symptoms related to hypocalcemia.
 
	

hypotension, tetany, cardiac arrhythmias) in the presence of hypocalcemia	
 
Administer calcium gluconate 50 to 100 mg/kg IV slowly with ECG monitoring unless hyperphosphatemia in which case should address in consultation with nephrology.
 
Recheck potassium, phosphorous, uric acid, calcium, and creatinine in 1 hour after administration of calcium gluconate. If calcium normalizes 1 hour later, repeat potassium phosphorous, uric acid, calcium, and creatinine 2 and 4 hours later, if no other evidence of tumor lysis.
 
	
Event	Hyperphosphatemia	
Phosphate ≥ 0.5 mg/dL (1.615 mmol/L) with ≥ 5.0 mg/dL (0.16 mmol/L) increase	
 
Hold camonsertib (RP-3500) and olaparib until resolution to < 5.0 mg/dL (1.615 mmol/L).
 
Administer a phosphate binder (e.g., aluminium)
 
Recheck potassium, phosphorous, uric acid, calcium, and creatinine in 1 hour after administration of phosphate binder. If calcium normalizes 1 hour later, repeat potassium phosphorous, uric acid, calcium, and creatinine 2 and 4 hours later, if no other evidence of tumor lysis.
 
	

For blood chemistry changes or symptoms suggestive of TLS outside of cycle 1:

- Withhold the next day's dose of RP-3500 and olaparib. If it resolves within 48 hours of last dose resume at the same dose and then proceed with planned therapy.
- For any blood chemistry changes requiring > 48 hours to resolve and TLS attributable to RP-3500 and olaparib treatment, resume both drugs at one DL lower.
- For any events of clinical TLS and attributable to RP-3500 and olaparib treatment, hold both drugs and provide best supportive care. When resolved, resume both drugs at one DL lower.

If TLS does not re-occur after 2 weeks of treatment at the reduced doses, increase of both drugs to the prior DL can be considered. Should laboratory or clinical TLS re-occur after re-escalation to the higher DL, and is attributable to RP-3500 and olaparib treatment, both drugs should be permanently lowered to one DL lower.

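### In the cycle 1 tumor lysis table, symptomatic potassium of 6 mmol/L or more together with high uric acid draws incompatible rescue instructions, and some potassium values above the upper limit of normal fit no potassium row

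*Combined protocol and SAP*

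**What the plan says.** The protocol's section 6.6.4 contains a management table introduced with "For blood chemistry changes or symptoms suggestive of TLS in cycle 1". Three of its potassium and uric acid features matter here.

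- **Potassium, top row.** The third potassium row is triggered by "Potassium ≥ 6 mmol/L (6.0mEq/L) and symptomatic". Among its steps: "Administer sodium bicarbonate 1 to 2 mEq/kg IV. Rasburicase should not also be used as this may exacerbate calcium phosphate precipitation".
- **Uric acid rows.** There are two. One starts at 8.0 mg/dL. The other starts at 10 mg/dL, or at 8.0 mg/dL with a 25% rise and a creatinine increase. Both contain the same order: "Give rasburicase (as per local guidelines). Sodium bicarbonate should not be used as this may exacerbate calcium phosphate precipitation".
- **Other potassium rows.** The first covers a rise of at least 0.5 mmol/L with the value still at or below ULN. The second is triggered by "Potassium > ULN but < 6 mmol/L (6.0mEq/L) and asymptomatic", but its heading then gives a bracketed list of symptoms as examples, the same list that follows the word symptomatic in the third row.

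All the rows described here hold both study drugs. The separate rules in section 6.6.4 for events outside cycle 1 deal with withholding and resuming study drug and do not address either point.

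**The concern.** The rows are written one analyte at a time, but the table expects analytes to be disturbed together. Its recheck steps ask for potassium, phosphorus, uric acid, calcium and creatinine as a set, and several rows depend on there being no other sign of tumor lysis. A patient who meets the third potassium row and a uric acid row is therefore within the table's own scope. For that patient, obeying one row means breaking the other.

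The potassium categories above ULN combine a level with a symptom condition, and the two pairings printed do not exhaust the possibilities. A site reading the table literally would find an instruction for a lower asymptomatic value and none for a higher one.

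What is at stake is consistent safety management at the two sites. Section 6.6.4 states that it is unknown whether the combination induces tumor lysis, and section 8.4 classifies the trial as high risk. Chemistry is drawn on cycle 1 days 1, 2 and 3, and section 7.6.3 shows that day 2 is a dosing day, so whether an instruction to hold applies can matter at once.

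**Working it through.** No sample size, error rate or event count is involved. The check is to compare the rows and enumerate the categories.

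**Step 1. Do the orders conflict?**

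| Row in the cycle 1 table | Study drugs | Bicarbonate | Rasburicase |
|---|---|---|---|
| Potassium row 1 (rise, at or below ULN) | hold | not mentioned | not mentioned |
| Potassium row 2 (above ULN, below 6, asymptomatic) | hold | not mentioned | not mentioned |
| Potassium row 3 (6 or more, symptomatic) | hold | ordered | excluded |
| Uric acid row 1 (8.0 mg/dL or more) | hold | excluded | ordered |
| Uric acid row 2 (10 mg/dL or more, or 8.0 with rises) | hold | excluded | ordered |

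Potassium row 3 paired with either uric acid row both orders and excludes each agent. Potassium rows 1 and 2 order neither agent, so they do not conflict with the uric acid rows. The conflict is therefore confined to one overlap: symptomatic potassium of 6 mmol/L or more with uric acid of 8.0 mg/dL or more. The study-drug instruction is the same in every row, so no conflict arises over holding treatment.

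**Step 2. Does another rule settle the overlap?** The nearest is in section 6.6.5, for a patient with several adverse events and conflicting recommendations. It chooses the study-drug dose adjustment giving the lowest dose. It says nothing about rescue agents. The authors did write a cross-analyte rule elsewhere in the same table: the hypocalcemia row makes an exception for hyperphosphatemia and sends it to nephrology. No such link joins potassium and uric acid.

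**Step 3. Are the potassium rows exhaustive above ULN?** Cross two levels with two symptom states:

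| Potassium | Asymptomatic | Symptomatic |
|---|---|---|
| above ULN, below 6 mmol/L | row 2 | no row, read literally |
| 6 mmol/L or more | no row | row 3 |

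Rows cover 2 of 4 cells, leaving 4 − 2 = 2 uncovered. The lower-left cell is uncovered on any reading. The upper-right cell is less certain, because the symptoms listed in row 2's heading leave its trigger unclear.

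**Step 4. What does the gap do?** Take an asymptomatic patient with normal values for the other analytes and a ULN below 5.9 mmol/L. At 5.9, row 2 applies: hold, ECG, recheck at 1 hour. At 6.1, no potassium row applies. Row 1 also sends some patients on to management for potassium above ULN, which is this incomplete set.

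**Step 5. Can a hold come from elsewhere?** Yes, in two ways. The uric acid, hypocalcemia and hyperphosphatemia rows each hold both drugs and recheck potassium, so a patient in an uncovered cell who also meets one of those rows gets a hold and a recheck. The last block of Table 14 in section 6.6.5 holds the causative agent for other non-hematologic toxicity of grade 3 or higher. That depends on how the potassium value is graded, and the protocol does not print the CTCAE threshold. It also depends on attribution, and it supplies no ECG and no timed recheck.

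**The case against.** The strongest reply is that each row is coherent alone. All three rows that mention these agents warn against combining them and give the same reason, so the table can be read as saying to use one and not the other. Only one of three potassium rows orders bicarbonate. Section 6.6 is headed as guidelines, rasburicase is left to local practice, and section 6.5 recommends consulting the study PI and medical monitor after significant events. This stands as a limit on scope: what is missing is a priority rule for one overlap. It does not remove the problem, because neither row says which agent to choose when both apply, and the consultation advice in section 6.5 concerns dosing.

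A second reply is that patients in the uncovered cells are not left without any hold. This also stands in part. The gap in hold, ECG and recheck is a gap in the tumor lysis table for isolated hyperkalemia. Row 1's use of potassium above ULN as a general category suggests that every such value was meant to be managed, which supports completing the rows.

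A reader might go further and infer that the sickest patients receive contradictory orders or none. The documents do not support that: the table's top potassium category, 6 or more with symptoms, has a full row. A reader might also infer that the overlap is common because tumor lysis usually raises both analytes. The documents give no frequency, and preventive xanthine oxidase inhibition is required in cycle 1.

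**Conclusion.** The inconsistency is real and limited. In the cycle 1 table, symptomatic potassium of 6 mmol/L or more combined with uric acid of 8.0 mg/dL or more gives incompatible instructions on the rescue agent, with no rule of priority. Holding study drug is not in dispute. Separately, asymptomatic potassium of 6 mmol/L or more has no potassium row, and symptomatic potassium between ULN and 6 has none on the literal reading: two of four cells. For isolated hyperkalemia in those cells the table itself triggers no hold, ECG or timed recheck. A hold may still follow from the grade 3 or higher rule, subject to grading and attribution.

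How many patients this would affect cannot be stated from the documents. It is tempting to connect the point to dose escalation, since the dose-limiting toxicity window is cycle 1 days 1 to 21 and section 4.2.4 exempts tumor lysis not requiring dialysis. Nothing in the documents links the choice of rescue agent to dialysis, so no effect on those counts is shown. No estimand, sample size or planned analysis is affected.

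The conclusion rests on the printed row triggers and takes no position on which treatment is right.

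**What to change.** Amend the cycle 1 table in section 6.6.4 in three places.

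1. Reconcile the third potassium row with the two uric acid rows, so that a patient who meets both has one consistent instruction.
2. Clarify the heading of the second potassium row, where a list of symptoms follows the word asymptomatic.
3. Make the potassium rows exhaustive, so that every value above ULN, with or without symptoms, maps to exactly one row.

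The sponsor and medical monitor should set the clinical content. The cost is a protocol amendment to one table, with no added visits or tests.

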## 6.6.5 Non-hematologic Toxicities

Specific guidelines are provided below for selected non-hematologic toxicities. In AEs that have guidelines for both RP-3500 and olaparib, follow the guideline for the most likely causative agent. If the causative agent cannot be determined, hold both RP-3500 and olaparib and follow the guidelines for both drugs.

If a patient experiences several adverse events, and there are conflicting recommendations, the investigator should use the recommended dose adjustment that reduces the dose to the lowest level. Treatment delays for adverse events exceeding 21 days will lead to protocol removal. If reduction of the drug doses resolves the patient's toxicity to grade  $\leq 1$  for at least 3 weeks,

increasing RP-3500 and/or olaparib back to the prior dose is permitted. No dose below dose level 1 (Table 11) for either drug is allowed and should protocol dictate another dose reduction below dose level 1, the patient will be removed from study.

Table 14. Management and dose modification guidelines for non-hematologic toxicities encountered with combination RP-3500 and olaparib.

Event Name	Nausea	
Grade of Event	Management/Next Dose for RP - 3500	Management/Next Dose for Olaparib
≤ Grade 1	No change in dose	5-HT3-antagonists, D2-antagonists or NK1 antagonists, and benzodiazepines administration can prevent or treat nausea in the majority of patients. Consider additional anti-emetics as per the NCCN Clinical Practice Guideline for antiemesis  . Advise patient to take one or more anti-nausea medications 30-60min prior to taking olaparib.
Grade 2	No change in dose. Modify dosing schedule of RP-3500 concurrently with olaparib.	Implement one or more combinations of anti-nausea medications including dexamethasone pre-medication given 30- 60 min prior to taking RP-3500 and olaparib. Consider additional anti-emetics as per the NCCN Clinical Practice Guideline for antiemesis  . Advise patient to take one or more anti-nausea medications 30-60min prior to taking olaparib. Olanzapine 2.5 to 5mg every morning, as per NCCN guidelines, can mitigate nausea/vomiting. If nausea persists at grade 2 for ≥7 days, hold olaparib. May resume olaparib at the same dose if nausea becomes ≤ grade 1. If grade 2 nausea reoccurs for ≥7 days for a second occurrence despite maximal supportive care, then follow reductions in dosing schedule and drug dosages as per sections 6.6.1 and 6.6.2. If patient's nausea is grade ≤1 for 3 weeks, then the dose or dosing schedule of olaparib may

		be increased back to the previous
		dose/schedule.
Grade 3	No change in dose. Modify dosing schedule of RP-3500 concurrently with olaparib.	Hold drug and implement one or more combinations of anti-nausea medications including dexamethasone pre-medication given 30-60 min prior to taking RP-3500 and olaparib. Consider additional anti- emetics as per the NCCN Clinical Practice Guideline for antiemesis  . May restart olaparib at the same dose level once nausea becomes ≤ grade 1 and advise the patient to take one or more anti-nausea medications 30-60min prior to taking olaparib. Olanzapine 2.5 to 5mg every morning, as per NCCN guidelines, can mitigate nausea/vomiting. If grade 3 nausea reoccurs, hold drug until nausea resolves to ≤ grade 1 and resume olaparib with a dose reduction following reductions in dosing schedule and drug dosages as per sections 6.6.1 and 6.6.2. If patient's nausea is grade ≤1 for 3 weeks at the reduced dose/schedule, then olaparib may be increased back to the previous dose/schedule.
Event Name	Va	omiting
Grade of Event	Management/Next Dose for RP - 3500	Management/Next Dose for Olaparib
≤ Grade 2	No change in dose	No change in dose. Implement one or more combinations of anti-nausea medications including dexamethasone pre-medication given 30-60 min prior to taking RP-3500 and olaparib. Consider additional anti-emetics as per the NCCN Clinical Practice Guideline for antiemesis  . Advise patient to take one or more anti-nausea medications 30- 60min prior to taking olaparib. Olanzapine 2.5 to 5mg every morning, as per NCCN guidelines, can mitigate nausea/vomiting.

Grade 3	No change in dose. Modify dosing schedule of RP-3500 concurrently with olaparib.	Hold until toxicity ≤ grade 1 and resume treatment with reduction of dosing following reductions in dosing schedule and drug dosages as per sections 6.6.1 and 6.6.2. Implement maximal supportive care measures including dexamethasone pre-medication 30-60 min prior to taking RP-3500 and olaparib. Olanzapine 2.5 to 5mg every morning, as per NCCN guidelines, can mitigate nausea/vomiting. If patient's vomiting is grade ≤1 for 3 weeks at the reduced dose/schedule, then olaparib may be increased back to the previous dose/schedule.
Event Name	Diarrhea	
Grade of Event	Management/Next Dose for RP - 3500	Management/Next Dose for Olaparib
≤ Grade 1	No change in dose	Rule out other causes of diarrhea, including infectious etiologies and drug effects. At the first sign of loose or abnormal stool, it is recommended that the patient be treated according to institutional standard of care. Maintain dose of olaparib.
Grade 2	No change in dose. Modify dosing schedule of RP-3500 concurrently with olaparib.	If diarrhea is present despite maximal anti- diarrheal medications, rule out other causes of diarrhea, including infectious etiologies and drug effects. Reduce olaparib following reductions in dosing schedule and drug dosages as per sections 6.6.1 and 6.6.2(i.e. dosing schedule with either sequential or concurrent decrease in olaparib dose level) until resolved to grade ≤1, then increase olaparib to prior dose and/or schedule. If toxicity recurs at grade ≥2, then reduce olaparib following reductions in dosing schedule and drug dosages as per sections 6.6.1 and 6.6.2. If patient is stable and diarrhea resolves (grade 0 or

		baseline) for 3 weeks, olaparib may be re- escalated to prior dose/schedule.
≥ Grade 3	No change in dose. Modify dosing schedule of RP-3500 concurrently with olaparib.	If diarrhea is present despite maximal anti- diarrheal medications, rule out other causes of diarrhea, including infectious etiologies and drug effects. Hold olaparib until toxicity is grade ≤1, then restart olaparib following reductions in dosing schedule and drug dosages as per sections 6.6.1 and 6.6.2 (i.e. dosing schedule with either sequential or concurrent decrease in olaparib dose level). If patient is stable and diarrhea resolves (grade 0 or baseline) for 3 weeks, olaparib may be re-escalated to prior dose/schedule.
Event Name	Fatigue	
Grade of Event	Management/Next Dose for RP - 3500 Management/Next Dose for Olaparib	
Grade 1	Maintain dose. Rule out other causes. If found to be anemic and symptomatic, consider transfusing even with hemoglobin >8g/dL. Consider adding dexamethasone 4- 8mg pre-medication on days of RP- 3500/olaparib administration.	Maintain dose. Rule out other causes. If found to be anemic and symptomatic, consider transfusing even with hemoglobin >8g/dL. Consider adding dexamethasone 4-8mg pre-medication on days of RP- 3500/olaparib administration.
Grade 2 lasting ≤7 days	As per NCCN guidelines, consider stimulants such as methylphenidate 5mg QD in the morning only. Consider adding dexamethasone 4- 8mg pre-medication on days of RP- 3500/olaparib administration.	As per NCCN guidelines, consider stimulants such as methylphenidate 5mg QD in the morning only. Consider adding dexamethasone 4-8mg pre-medication on days of RP-3500/olaparib administration.
Grade 2 lasting >7 days or grade ≥3	Rule out other causes. If found to be anemic and symptomatic, consider transfusing even for hemoglobin >8 g/dL. As per NCCN guidelines, consider stimulants such as methylphenidate 5mg QD in the morning only. Hold RP-3500 dosing until resolved to ≤ grade 1 or	Rule out other causes. If found to be anemic and symptomatic, consider Transfusing even for hemoglobin >8 g/dL. As per NCCN guidelines, consider stimulants such as methylphenidate 5mg QD in the morning only. Hold olaparib dosing until resolved to ≤ grade 1 or baseline. For first occurrence, restart

	baseline. For first occurrence, restart RP-3500 at current dose and schedule. For second occurrence, reduce RP-3500 and olaparib treatments following reductions in dosing schedule and drug dosages as per sections 6.6.1 and 6.6.2. Consider adding dexamethasone 4- 8mg pre-medication on days of RP- 3500/olaparib administration. If patient is stable and fatigue resolves (≤ grade 1 or baseline) for 3 weeks, RP-3500 may be re-escalated to prior dose.	olaparib at current dose and schedule. For second occurrence, reduce olaparib and RP-3500 treatment following reductions in dosing schedule and drug dosages as per sections 6.6.1 and 6.6.2. Consider adding dexamethasone 4-8mg pre-medication on days of RP-3500/olaparib administration. If patient is stable and fatigue resolves (≤ grade 1 or baseline) for 3 weeks, olaparib may be re-escalated to prior dose.		
Event Name	Dyspnea			
Grade of Event	Management/Next Dose for RP - 3500	Management/Next Dose for Olaparib		
Grade 1	No change in dose	Rule out other causes, including infection, primary pulmonary causes (i.e. embolism, effusion and edema), cardiac etiologies and drug effects. Consider transfusing even if patient's hemoglobin is >8g/dL. Maintain dose.		
≥ Grade 2	No change in dose. Modify dosing schedule of RP-3500 concurrently with olaparib.	Rule out other causes, including infection, primary pulmonary causes (i.e. embolism, effusion and edema), cardiac etiologies and drug effects. Consider transfusing even if patient's hemoglobin is >8g/dL. Hold olaparib until toxicity resolves to grade ≤1. Resume olaparib at the same dose and schedule. If toxicity reoccurs despite maximal supportive care or treatment of underlying cause, reduce olaparib and RP-3500 following reductions in dosing schedule and drug dosages as per sections 6.6.1 and 6.6.2. If patient's dyspnea is grade ≤1 for 3 weeks at the reduced dose, then olaparib may be increased back to the previous dose/schedule.		
Other Non-Hematologic Toxicity				
≥ Grade 3	Hold the causative agent until toxicity is ≤ grade 1 or baseline. Implement maximal supportive care and rule out other potential causes of that toxicity. If treatment delay is ≤7 days, restart at same dose or at a lower dose level			

upon investigator discussions. If treatment delay is >7 days but ≤21 days, restart treatments following reductions in dosing schedule and drug dosages as per sections 6.6.1 and 6.6.2 in which changes in dosing schedule of both drugs should first be implemented with either sequential or concurrent reductions in drug dosages. If treatment delay >21 days, discontinue study.

